6.3. Changes From Protocol-Specified Efficacy Analyses

Change from baseline in \log_{10} (HBV DNA) (IU/mL), \log_{10} (HBsAg) (IU/mL), and ALT were added in the SAP as secondary efficacy endpoints to fully explore the treatment effect of TAF versus TDF.

Randomized Analysis Set was not defined in the protocol but is added in the SAP.

7. SAFETY ANALYSES

For Week 48 analysis, safety data will be summarized for the double-blind phase only up to Week 96. The upper limit of the least frequent schedule analysis window of Week 96 (Study Day 839) will be used as Week 96 data cut for cumulative summaries of safety events (eg, treatment-emergent AEs, treatment-emergent laboratory abnormalities). All safety data up to the Week 48 data-cut including data collected during the open-label phase and the 24-week treatment-free follow-up period will be included in data listings.

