Test Product, Dose, and Mode of Administration:

Double-Blind Treatment:

- Tenofovir alafenamide (TAF) 25 mg QD, oral administration and matched placebo of Tenofovir DF (TDF) 300 mg QD, oral administration

Open-Label Treatment:

- Tenofovir alafenamide (TAF) 25 mg QD, oral administration
-

Reference Therapy, Dose, and Mode of Administration:

Double-blind Treatment:

- Tenofovir DF 300 mg QD, oral administration and matched placebo of Tenofovir alafenamide (TAF) 25 mg QD, oral administration

Open-label Treatment: NA

Criteria for Evaluation:

Safety:

Key secondary safety endpoints include the percent change from baseline at Week 48 in hip and spine BMD, and change from baseline at Week 48 in serum creatinine.

If a subject has confirmed creatinine clearance (CL_{Cr}) < 50 mL/min, and $> 20\%$ decline in eGFR by CKD-EPI (cystatin C), at any time during the double-blind period of the study, the subject will be required to undergo dose modification to every other day dosing of study drug. Subjects with confirmed creatinine clearance < 30 mL/min at any time during the study will have the study drug permanently discontinued.

The proportion of subjects in each treatment arm with tolerability failure (defined as an adverse event [AE] leading to permanent discontinuation of study drug) at Weeks 48, 96, 144, 240, and 384 will be summarized. Change from baseline in serum creatinine will be assessed at every visit and summarized through Week 384/ED. Change from baseline in BMD by DXA of the spine and hip will be assessed at Weeks 24, 48, 72, 96, 120, and 144, and every 48 weeks until Week 384/ED. Fracture Risk Assessment will be evaluated at Baseline.

Ophthalmologic changes from baseline by fundoscopic examination at Weeks 24, 48, 72, 96, and 144 (or ED if prior to Week 144 and more than 24 weeks since the last exam) will be summarized for a subset of subjects ($n = 30$). In addition, for any subject who develops signs or symptoms of posterior uveitis, the investigator should contact the Gilead Medical Monitor to discuss the need for additional ophthalmologic evaluation including dilated funduscopy and optical coherence tomography (OCT).

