1.1. Study Objectives

The primary objectives of this study are as follows:

- To compare the efficacy of TAF 25 mg versus TDF 300 mg once daily for the treatment of hepatitis B e antigen (HBeAg)-negative, CHB at Week 48 in treatment-naïve and treatment-experienced subjects. The primary efficacy parameter is the proportion of subjects with plasma HBV DNA levels below 29 IU/mL
- To compare the safety and tolerability of TAF 25 mg once daily versus TDF 300 mg once daily for the treatment of HBeAg-negative, CHB at Week 48 in treatment-naïve and treatment-experienced subjects

The key secondary safety objectives of this study are as follows:

- To compare the safety of TAF 25 mg once daily versus TDF 300 mg once daily as determined by the percent change from baseline in hip and spine bone mineral density (BMD) at Week 48
- To compare the safety of TAF 25 mg once daily versus TDF 300 mg once daily as determined by the change from baseline in serum creatinine at Week 48
- To compare the safety of TAF 25 mg once daily versus TDF 300 mg once daily as determined by treatment-emergent proteinuria through Week 48

Other secondary objectives of this study are as follows:

- To compare the efficacy of TAF 25 mg once daily versus TDF 300 mg once daily for the treatment of HBeAg-negative, CHB in regard to the proportion of subjects with plasma HBV DNA levels below 29 IU/mL at Week 96, and 144
- To compare the efficacy of TAF 25 mg once daily versus TDF 300 mg once daily for the treatment of HBeAg-negative, CHB in regard to the proportion of subjects with plasma HBV DNA levels below 29 IU/mL (target not detected) at Weeks 48, 96, and 144
- To compare the biochemical (alanine aminotransferase [ALT] normalization) response of TAF 25 mg once daily versus TDF 300 mg once daily for the treatment of HBeAg-negative, CHB at Weeks 48, 96, and 144
- To compare the serological response (loss of hepatitis B surface antigen [HBsAg] with seroconversion to antibody to HBsAg [anti-HBs]) of TAF 25 mg once daily versus TDF 300 mg once daily for the treatment of HBeAg-negative, CHB at Weeks 48, 96, and 144
- To compare the change in fibrosis as assessed by FibroTest[®] of TAF 25 mg once daily versus TDF 300 mg once daily for the treatment of HBeAg-negative, CHB at Weeks 48, 96, and 144
- To compare the incidence of drug resistant mutations of TAF 25 mg once daily versus TDF 300 mg once daily at Weeks 48, 96, and 144

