3.7.2. Analysis Windows

Subject visits might not occur on protocol specified days. Therefore, for the purpose of analysis, observations will be assigned to analysis windows.

The following windows (Table 3-2 to Table 3-8) apply to baseline and on-treatment assessments only, ie, data collected up to the last dose date for those who discontinued study drug prematurely (except efficacy data [HBV DNA, quantitative HBsAg, HBV serology, ALT, fibrotest score] for subjects who discontinue study drug after Week 48 due to HBsAg loss with confirmed seroconversion to anti-HBs), or data collected up to database finalization date for those who have not discontinued study drug permanently.

For subjects who discontinue study drug early due to HBsAg loss with confirmed seroconversion, all efficacy data including data collected after the last dose date of the study drug will be reassigned analysis visits using the on-treatment assessment windows (Table 3-2, Table 3-3, and Table 3-5).

The analysis windows for HBV DNA, hematology, serum chemistry and liver function tests, urinalysis, urine pregnancy test, eGFR (by CG and Chronic Kidney Disease Epidemiology Collaboration [CKD-EPI]), renal biomarkers urine albumin to creatinine ratio (UACR), urine protein to creatinine ratio (UPCR), renal tubular maximum reabsorption rate of phosphate to the glomerular filtration rate (TmP/GFR), urine fractional excretion of filtered phosphate (FEPO₄), fractional excretion of uric acid (FEUA), weight, and vital sign assessments are presented in Table 3-2.

Table 3-2. Analysis Windows for HBV DNA, Hematology, Serum Chemistry and Liver Function Tests, Urinalysis, Urine Pregnancy Test, eGFR (by CG and CKD-EPI), PTH, UACR, UPCR, TmP/GFR, FEPO₄, FEUA, Weight, and Vital Sign Assessments

Visit ID	Nominal Day	Lower Limit	Upper Limit
Baseline			1
Week 4	28	2	41
Week 8	56	42	69
Week 12	84	70	97
Week 16	112	98	125
Week 20	140	126	153
Week 24	168	154	181
Week 28	196	182	209
Week 32	224	210	237
Week 36	252	238	265
Week 40	280	266	293
Week 44	308	294	321
Week 48	336	322	363
Week 56	392	364	419
Week 64	448	420	475
Week 72	504	476	531
Week 80	560	532	587
Week 88	616	588	643
Week 96	672	644	713
Week 108	756	714	797
Week 120	840	798	881
Week 132	924	882	965
Week 144	1008	966	1091
Week 168	1176	1092	1259
Week 192	1344	1260	1427
Week 216	1512	1428	1595
Week 240	1680	1596	1763
Week 264	1848	1764	1931
Week 288	2016	1932	2099
Week 312	2184	2100	2267
Week 336	2352	2268	2435
Week 360	2520	2436	2603

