Week 384	2688	2604	2771

The analysis windows for safety ECG and fibrotest are presented in Table 3-3.

Table 3-3. Analysis Windows for Safety ECG and Fibrotest

Visit ID	Nominal Day	Lower Limit	Upper Limit
Baseline			1
Week 48	336	2	503
Week 96	672	504	839
Week 144	1008	840	1175
Week 192	1344	1176	1511
Week 240	1680	1512	1847
Week 288	2016	1848	2183
Week 336	2352	2184	2519
Week 384	2688	2520	2855

The analysis windows for BMD results from DXA, and fasting lipid panel including direct low density lipoprotein (LDL), high density lipoprotein (HDL) and total cholesterol to HDL ratio, are presented in Table 3-4.

Table 3-4. Analysis Windows for BMD Results from DXA and Fasting Lipid Panel

Visit ID	Nominal Day	Lower Limit	Upper Limit
Baseline			1(14 ^a)
Week 24	168	2(15a)	251
Week 48	336	252	419
Week 72	504	420	587
Week 96	672	588	839 (755 ^b)
Week 120 ^b	840	756b	923b
Week 144	1008	840 (924 ^b)	1175
Week 192	1344	1176	1511
Week 240	1680	1512	1847
Week 288	2016	1848	2183
Week 336	2352	2184	2519
Week 384	2688	2520	2855

a This applies to DXA only. Upper limit for baseline DXA BMD is Day 14 and lower limit for Week 24 DXA BMD is Day 15.

b This applies to the subjects who consented to Amendment 3.1.

The analysis windows for serum HBsAg (quantitative) and HBV serology are presented in Table 3-5.

Table 3-5. Analysis Windows for Serum HBsAg (Quantitative) and HBV Serology

Visit ID	Nominal Day	Lower Limit	Upper Limit
Baseline			1
Week 12	84	2	125
Week 24	168	126	209
Week 36	252	210	293
Week 48	336	294	391
Week 64	448	392	503
Week 80	560	504	615
Week 96	672	616	713
Week 108	756	714	797
Week 120	840	798	881
Week 132	924	882	965
Week 144	1008	966	1091
Week 168	1176	1092	1259
Week 192	1344	1260	1427
Week 216	1512	1428	1595
Week 240	1680	1596	1763
Week 264	1848	1764	1931
Week 288	2016	1932	2099
Week 312	2184	2100	2267
Week 336	2352	2268	2435
Week 360	2520	2436	2603
Week 384	2688	2604	2771

The analysis windows for fasting glucose, fasting total cholesterol, fasting triglycerides, renal biomarkers including urine retinol binding protein (RBP) to creatinine ratio, urine beta-2-microglobulin to creatinine ratio, and bone biomarkers including C-type collagen sequence (CTX), procollagen type 1 N-terminal propeptide (P1NP), osteocalcin (OC), and bone specific alkaline phosphatase (bsAP) are presented in Table 3-6.

Table 3-6. Analysis Windows for Fasting Glucose, Fasting Total Cholesterol, Fasting Triglycerides, Renal, and Bone Biomarkers

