7.4.4. Treatment-Emergent Proteinuria (Dipstick)

Treatment-emergent proteinuria by urinalysis (dipstick) through Week 48 will be summarized by treatment group. A listing of subjects with treatment-emergent proteinuria will be provided.

7.4.5. Urine Creatinine, Urine RBP to Creatinine Ratio and Beta-2-microglobulin to Creatinine Ratio

Baseline, postbaseline, change from baseline and percentage change from baseline in urine creatinine, urine RBP to creatinine ratio and beta-2-microglobulin to creatinine ratio will be summarized by treatment group and visit using descriptive statistics. Median (Q1, Q3) percentage change from baseline over time will be plotted by treatment group.

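### In the China Week 48 analysis, no adverse-event table and no general graded laboratory table is cut at Week 48: all can run to Study Day 839, and Week 48 tolerability failure is not produced

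*SAP*

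**What the plan says.** SAP 1.1 sets the second primary objective as safety and tolerability "for the treatment of HBeAg-negative, CHB at Week 48 in treatment-naïve and treatment-experienced subjects". The same section lists safety and tolerability beyond Week 48 of the double-blind phase as a separate secondary objective, which SAP 7.11 declares as an addition.

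SAP 7 sets the horizon for the tables: "For Week 48 analysis, safety data will be summarized for the double-blind phase only up to Week 96". For cumulative summaries, with treatment-emergent AEs and laboratory abnormalities as the examples, it adds: "The upper limit of the least frequent schedule analysis window of Week 96 (Study Day 839) will be used as Week 96 data cut". SAP 2.2 triggers the analysis once the last subject has completed the Week 48 visit or stopped study drug. SAP 1.2 says the China subjects stay on blinded treatment for three years.

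One event summary has a Week 48 horizon, in SAP 7.4.4: "Treatment-emergent proteinuria by urinalysis (dipstick) through Week 48 will be summarized by treatment group". SAP 7.4.2 also summarizes change in serum creatinine at Week 48. Numeric laboratory results, bone mineral density, eGFR, ECG and weight are summarized by visit.

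The Protocol synopsis (Criteria for Evaluation, Safety) defines tolerability failure as an adverse event "leading to permanent discontinuation of study drug) at Weeks 48, 96, 144, 240, and 384 will be summarized".

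**The concern.** A table read as the answer to a Week 48 objective should count events up to Week 48. Tables 26-44 in SAP Appendix 1 cover treatment-emergent AEs, SAEs, AEs leading to discontinuation, graded laboratory abnormalities and ALT elevations. They count whatever has occurred on blinded drug up to Day 839. Subjects enrolled early contribute more time than those enrolled late, and all enter one crude percentage. That percentage depends on how fast China enrolled.

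Two things are at stake. The Week 48 safety objective and the beyond-Week-48 objective would share one set of tables, so the first could not be read from them. And an output named in the protocol, the Week 48 tolerability-failure proportion, would be missing without being listed among the changes in SAP 7.11.

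**Working it through.** **Where Day 839 comes from.** In the SAP window tables the upper limit is the midpoint between adjacent nominal days, minus 1. The least frequent schedule is the one for ECG and FibroTest (Table 3-3), where Week 96 is Day 672 and the next visit, Week 144, is Day 1008: (672 + 1008)/2 − 1 = 839. The SAP's figure is reproduced exactly.

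**What it means in time.**
- 839/7 = 119.9 weeks, which is 839/336 = 2.50 times the nominal Week 48 (Day 336).
- It lies (839 − 672)/7 = 23.9 weeks after nominal Week 96 and one day before nominal Week 120 (Day 840).
- In Table 3-2, which covers most laboratory tests, the Week 96 row reads "Week 96 672 644 713" (nominal day, lower limit, upper limit). That window closes on Day 713, and Day 839 lies inside the Week 120 window (Days 798 to 881).

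**Who reaches it.** Day 839 is a ceiling. If the data are cut at the last subject's Week 48, a subject reaches it only if first dosed (839 − 336)/7 = 71.9 weeks or more before the last subject.

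**Direction.** A subject with an event by Week 48 is also counted in the longer table, so the longer percentage cannot be lower over the same denominator. This needs no model.

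**Size, by illustration.** Assume uniform accrual over A weeks, a cut at the last subject's Week 48, constant hazard h and no dropout. Follow-up is then uniform from 48 to 48 + A weeks (capped at 119.9), with mean 48 + A/2, and

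expected crude incidence = 1 − [exp(−48h) − exp(−(48 + A)h)]/(A·h), where h = −ln(1 − p48)/48.

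For p48 = 5% and A = 24: h = 0.051293/48 = 0.0010686 per week; exp(−48h) = 0.9500; exp(−72h) = 0.92595; A·h = 0.025647. The result is 1 − 0.02405/0.025647 = 0.062.

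| Accrual A (assumed) | Mean follow-up | True 5% at Week 48 appears as | True 20% at Week 48 appears as |
|---|---|---|---|
| 24 weeks | 60 weeks | 6.2% | 24% |
| 52 weeks | 74 weeks | 7.6% | 29% |
| 72 weeks | 84 weeks | 8.6% | 32% |

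On the same assumptions, a true 10% appears as 12.5% with 26 weeks of accrual and 18.7% with 104. If every subject reached Day 839 it would appear as 23.1%.

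**Which tables have a Week 48 cut.**

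| Output | Horizon in the SAP |
|---|---|
| AE tables (26-40) | Up to at most Day 839 |
| Graded laboratory abnormalities (41-43), ALT elevation (44) | Up to at most Day 839 |
| Dipstick proteinuria (58) | Through Week 48 |
| Numeric laboratory data, creatinine, bone mineral density, eGFR | By visit, including Week 48 |
| Tolerability failure at Week 48 | Not planned; Table 36 is cumulative |

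**The case against.** The best defence is that cumulative reporting follows the protocol. Protocol 8.6 asks for all safety data up to the last dose to be summarized by treatment group, and Protocol 8.6.3 and 8.6.4 define treatment-emergence with no Week 48 limit. The SAP discloses the longer horizon and has an objective that uses it. Exposure by arm and Kaplan-Meier time to premature discontinuation are tabulated (SAP 4.3.1), AEs are listed, and the safety summaries are descriptive. All of this stands, and it supports keeping the long tables. It does not supply a Week 48 incidence: the Kaplan-Meier analysis covers discontinuation for any reason, and no exposure-adjusted or time-to-event AE analysis is planned.

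A reader might infer more than the documents support:
- **That the Week 48 analysis gives no Week 48 safety result.** Dipstick proteinuria and the by-visit summaries do, although by-visit means and shifts are not event incidences.
- **That subjects are followed for 120 weeks.** That is a maximum, and with short accrual few or none would reach it.
- **That Day 839 is a miscalculation.** It follows the SAP's stated rule; the difficulty is applying an ECG and FibroTest window to AEs and laboratory tests.
- **That the comparison of arms is biased.** Randomization makes the staggering similar in both arms in expectation.
- **That differing accrual distorts a China versus non-China safety comparison.** Neither cohort's accrual pattern is given, and this SAP plans no such comparison.

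**Conclusion.** The point holds as one of completeness and labelling. As written, the plan gives no AE, general graded laboratory or ALT-elevation table cut at Week 48, and it omits the synopsis's Week 48 tolerability-failure proportion. The conflict is with the Week 48 objective and that synopsis summary, not with Protocol 8.6.

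The direction is certain: the reported percentages equal or exceed the Week 48 incidence in both arms. The size is not known, because the accrual period is not in the documents. The illustrated shift, from 5% to between 6.2% and 8.6%, rests on uniform accrual of 24 to 72 weeks, constant hazard and no dropout. Dropout would reduce it, since follow-up for treatment-emergent events largely ends when drug stops. Events concentrated early would also reduce it, and events that build up late would increase it.

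**What to change.** In SAP 7 and Appendix 1, add Week 48 versions of the AE, SAE, AE-leading-to-discontinuation and graded laboratory tables, including ALT elevation.

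- **AEs:** cut at one prespecified day, for example Day 363, the Week 48 upper limit in Table 3-2. That table does not list AEs, so the day must be stated as a choice.
- **Laboratory tests:** cut at each parameter's own Week 48 upper limit. This is Day 363 for tests in Table 3-2 and Day 419 for fasting lipids and glucose (Tables 3-4 and 3-6). A single Day 363 cut would drop fasting results that the SAP assigns to Week 48.
- **Both:** stop at the last blinded dose if that is earlier.
- **Tolerability failure:** report AEs leading to permanent discontinuation by the AE cut as the Week 48 proportion.

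Do not carry the least-frequent-window rule over to Week 48. It would give (336 + 672)/2 − 1 = Day 503, or 71.9 weeks.

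Keep the existing tables as supportive for the beyond-Week-48 objective, and describe their cut as all available double-blind data up to Day 839. The cost is a few lines of SAP text and one extra run of the existing table programs. No data are lost.

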7.1. Adverse Events

7.1.1. Adverse Event Dictionary

AEs will be coded using the Medical Dictionary for Regulatory Activities (MedDRA). System Organ Class (SOC), high-level group term (HLGT), high-level term (HLT), preferred term (PT), and lower-level term (LLT) will be attached to the clinical database.

7.1.2. Adverse Event Severity

AEs are graded by the investigator as Grade 1 (mild), Grade 2 (moderate), Grade 3 (severe) or Grade 4 (life threatening) according to toxicity criteria specified in Appendix 5 of the clinical study protocol. The severity grade of events for which the investigator did not record severity will be categorized as “missing” for tabular summaries and data listings, and will be considered the least severe for the purposes of sorting for data presentation.

7.1.3. Relationship of AEs to Study Drug

Related AEs are those for which the investigator answers “Yes” to the question “Related to Study Treatment?” in the eCRF. Events for which the investigator did not record relationship to study drug will be considered related to study drug for summary purpose. Data listings will show relationship as missing.

7.1.4. Relationship of AEs to Study Procedure

AEs for which ‘Yes’ is marked for question ‘Related to Study Procedures?’ in the eCRF will be identified and included in AE listing.

7.1.5. Serious AEs

Serious AEs are those identified as serious in the eCRF, where ‘Yes’ was marked for ‘AE serious’. The clinical database will be reconciled with the serious AE database (from the Drug Safety and Public Health Department) before database finalization.

7.1.6. Treatment-Emergent AEs

7.1.6.1. Definition of Treatment-Emergent

Treatment-emergent AEs occurring during the double-blind phase are defined as:

- Any AE with an onset date on or after the blinded study drug start date and no later than the study drug stop date for those who discontinued blinded study drug permanently, or
- Any AE with an onset date on or after the blinded study drug start date for those who remain on the blinded study drug, or
- Any AE leading to blinded study drug discontinuation.

Treatment-emergent AEs occurring during the open-label phase are defined as:

- Any AE with an onset date on or after the open-label study drug start date and no later than the open-label study drug stop date for those who discontinued open-label study drug permanently, or
- Any AE with an onset date on or after the open-label study drug start date for those who remain on the open-label study drug, or
- Any AE leading to open-label study drug discontinuation.

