7. ADVERSE EVENTS AND TOXICITY MANAGEMENT

7.1. Definitions of Adverse Events, Adverse Reactions, and Serious Adverse Events

7.1.1. Adverse Events

An adverse event (AE) is any untoward medical occurrence in a clinical study subject administered a medicinal product, which does not necessarily have a causal relationship with the treatment. An AE can therefore be any unfavorable and/or unintended sign, symptom, or disease temporally associated with the use of a medicinal product, whether or not considered related to the medicinal product. AEs may also include pre- or post-treatment complications that occur as a result of protocol specified procedures, lack of efficacy, overdose, drug abuse/misuse reports, or occupational exposure. Preexisting events that increase in severity or change in nature during or as a consequence of participation in the clinical study will also be considered AEs.

An AE does not include the following:

- Medical or surgical procedures such as surgery, endoscopy, tooth extraction, and transfusion. The condition that led to the procedure may be an adverse event and must be reported.
- Pre-existing diseases, conditions, or laboratory abnormalities present or detected before the screening visit that do not worsen
- Situations where an untoward medical occurrence has not occurred (e.g., hospitalization for elective surgery, social and/or convenience admissions)
- Overdose without clinical sequelae (see Section 7.6.1)
- Any medical condition or clinically significant laboratory abnormality with an onset date before the consent form is signed and not related to a protocol-associated procedure is not an AE. It is considered to be pre-existing and should be documented on the medical history CRF.

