8.6.3. Adverse Events

Clinical and laboratory adverse events will be coded using the Medical Dictionary for Regulatory Activities (MedDRA). System Organ Class (SOC), High-Level Group Term (HLGT), High-Level Term (HLT), Preferred Term (PT), and Lower-Level Term (LLT) will be attached to the clinical database.

Events will be summarized on the basis of the date of onset for the event. A treatment-emergent adverse event will be defined as any adverse event that begins on or after the date of first dose of treatment up to the date of last dose of treatment. Continuing adverse events diagnosed prior to the start of treatment and worsening in severity grade, or non-serious adverse events at baseline which become serious, or adverse events resulting in treatment discontinuation after the start of treatment will also be considered treatment-emergent.

Summaries (number and percentage of subjects) of treatment-emergent adverse events (by SOC, and PT) will be provided by treatment group:

- Treatment-emergent adverse events
- Treatment-emergent study drug-related adverse events
- Grade 3 or 4 treatment-emergent adverse event
- Grade 3 or 4 treatment-emergent study drug-related adverse event
- Grade 2, 3, or 4 treatment-emergent adverse event
- Grade 2, 3, or 4 treatment-emergent study drug-related adverse event
- AE that caused permanent discontinuation from study drug
- AE that caused change in dose or temporary interruption of study drug
- Treatment-emergent serious adverse event
- Treatment-emergent study drug-related serious adverse event

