7.1.7. Summaries of AEs and Deaths

A brief summary of AEs (ie, the number and percentage of subjects) will be presented by treatment group for the following: (1) any treatment-emergent AE, (2) any Grade 3 or 4 treatment-emergent AE, (3) any Grade 2, 3 or 4 treatment-emergent AE, (4) any treatment-emergent study drug-related AE, (5) any Grade 3 or 4 treatment-emergent study drug-related AE, (6) any Grade 2, 3 or 4 treatment-emergent study drug-related AE, (7) any treatment-emergent serious adverse event (SAE), (8) any treatment-emergent study drug-related SAE,

- (9) any treatment-emergent AE leading to premature study drug discontinuation,
- (10) any treatment-emergent AE leading to dose modification or study drug interruption, and
- (11) any treatment-emergent death.

Treatment-emergent death refers to death that occurs between the first dose date and the last dose date (inclusive).

Summaries (number and percentage of subjects) of AEs (by SOC, HLT [if specified below], and PT) will be provided by treatment group and overall using the Safety Analysis Set as follows:

- All treatment-emergent AEs summarized by SOC, HLT, and PT
- Any Grade 3 or 4 treatment-emergent AEs
- Any Grade 2, 3, or 4 treatment-emergent AEs
- All treatment-emergent nonserious AEs occurring in at least 5% of subjects in any treatment group (this summary is generated per requirement for reporting in ClinicalTrials.gov)
- All treatment-emergent study drug-related AE summarized by SOC, HLT, and PT
- Any Grade 3 or 4 treatment-emergent study drug-related AEs
- Any Grade 2, 3, or 4 treatment-emergent study drug-related AEs
- All treatment-emergent SAEs
- All treatment-emergent study drug-related SAEs
- All treatment-emergent AEs leading to premature discontinuation from study drug
- All treatment-emergent AEs leading to dose modification or study drug interruption

Multiple events will be counted once only per subject in each summary. For data presentation, SOC (and HLT) will be ordered alphabetically, with PT sorted by decreasing total frequency. For summaries by severity grade, the most severe event will be selected.

In addition to the by-treatment summaries, data listings will be provided for the following:

- All AEs
- Grade 3 and 4 AEs
- SAEs

- Study drug-related SAEs
- Deaths
- AEs leading to premature discontinuation of study drug
- AEs leading to dose modification or study drug interruption

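### SAP 7.1.6.1 drops, without declaring it, two of the protocol's four routes to treatment-emergent status: pre-treatment AEs that worsen in grade and non-serious baseline AEs that become serious

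*SAP*

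**What the plan says.** Protocol 8.6.3 starts from onset on treatment, "any adverse event that begins on or after the date of first dose of treatment up to the date of last dose of treatment". It then widens the definition to "Continuing adverse events diagnosed prior to the start of treatment and worsening in severity grade, or non-serious adverse events at baseline which become serious", and closes by saying that "adverse events resulting in treatment discontinuation after the start of treatment will also be considered treatment-emergent". That makes four routes.

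SAP 7.1.6.1, for the double-blind phase, has three bullets:

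- For subjects off blinded drug: "Any AE with an onset date on or after the blinded study drug start date and no later than the study drug stop date".
- For subjects still on it: "Any AE with an onset date on or after the blinded study drug start date for those who remain on the blinded study drug".
- "Any AE leading to blinded study drug discontinuation".

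SAP 7.1.6.2 adds rules for incomplete or missing onset dates. SAP 7.1.7 builds its summaries on this definition, for example "All treatment-emergent SAEs". The uveitis, cardiovascular, fracture and bone-event summaries (SAP 7.1.8, 7.1.9, 7.3.3 and 7.3.5) use the same term.

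SAP 7.11 lists the departures from the protocol's safety analyses. It has three entries: proteinuria as an added key secondary endpoint, no ophthalmologic analysis, and an added objective on safety after Week 48. The treatment-emergent definition is not among them.

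**The concern.** The two documents give different answers to the question of which events count. Safety and tolerability at Week 48 is a primary objective (Protocol 2, SAP 1.1), and the AE tables are the main evidence on it. Dropping two routes can only lower the counts. The events at risk are a grade increase on drug and a conversion to serious on drug. A reader of the study report who has the protocol, and sees nothing in SAP 7.11, would take the tables to follow the protocol definition.

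The omission does not look like a general decision to ignore worsening. SAP 7.2.2.1 and 7.2.2.2 keep worsening from baseline as the criterion for laboratory abnormalities. Only clinical AEs lose it.

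**Working it through.** No arithmetic applies: the plan states no count or rate for these events. The check is a comparison of the texts.

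**Step 1. Routes to treatment-emergent status.**

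| Route | Protocol 8.6.3 | SAP 7.1.6.1 |
|---|---|---|
| Onset on treatment | yes | yes |
| Continuing pre-treatment event worsens in grade | yes | no |
| Non-serious baseline event becomes serious | yes | no |
| Event leads to stopping drug | yes | yes |

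Two of the four are absent. SAP 7.1.6.2 does not restore them, since it deals only with incomplete or missing onset dates.

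**Step 2. What reaches the AE form with a pre-dose date.** Protocol 6.2.1 and 7.3 put only SAEs and procedure-related AEs on the AE form between consent and first dose. Protocol 6.2.1 sends everything else, exacerbations included, to the medical history form. For the becoming-serious route, the pre-dose AE-form pool is therefore only non-serious, procedure-related AEs from a screening period of up to 45 days. For the worsening route it is screening SAEs and procedure-related AEs. Separately, Protocol 7.1.1 extends its definition of an AE with this sentence: "Preexisting events that increase in severity or change in nature during or as a consequence of participation in the clinical study will also be considered". Under it, a medical-history condition that worsens on study becomes an AE. The documents do not say which onset date its record carries.

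**Step 3. Apply both definitions to an event that worsens or turns serious on blinded drug.**

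| Case | Protocol | SAP |
|---|---|---|
| AE-form record, complete pre-dose onset date, drug continued | counted | not counted |
| Same, but drug stopped because of the event | counted | counted |
| Onset date wholly missing, end date missing or not before first dose | counted | counted |
| Partial onset date in the month (or year) of first dose, end date missing or not before first dose | counted | counted |
| Medical-history condition, new AE record dated at worsening | counted | counted |
| Medical-history condition, AE record keeps its original onset date, drug continued | counted | not counted |

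The loss is confined to the first and last rows.

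**Step 4. Which outputs can change.** In SAP Appendix 1, the tables that can lose an event are 26 to 35, 37 to 40, 52 and 54. Table 36 (AEs that led to stopping drug) cannot change, because every such event qualifies under both definitions. Nor can the treatment-emergent death count, which SAP 7.1.7 defines by date of death. The graded laboratory tables (41 to 43) follow their own rule. The listings of all AEs, Grade 3 and 4 AEs and SAEs keep every event.

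**The case against.** The strongest case on the other side is that this is a wording mismatch with almost no events behind it. The pool of pre-dose records on the AE form is very narrow. The commoner situation, a medical-history condition that gets worse, may already be counted if sites enter it as a new AE. The AE summaries are counts and percentages with no hypothesis test, the same rule applies to both arms, and nothing disappears from the listings. This SAP covers only the Week 48 analysis of the roughly 150 subjects in China. Restoring the routes may also be less simple than it looks: SAP 7.1.2 and 7.1.5 describe an investigator grade and a serious flag, with no dated history of either.

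Most of this stands as a limit on size, and the programming point has to be met in the fix. It does not remove the contradiction. It also shows that the SAP count depends on an unstated dating convention: two sites could handle the same worsening differently and only one event would be tabulated. Under the protocol's routes both would be counted.

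Two stronger readings are tempting and should not be drawn. A reader might infer that all such events vanish from every treatment-emergent table; Steps 3 and 4 show that they do not. A reader might also try to size the loss from the SAE rates in the cited HIV Phase 2 study (5.4% and 3.4%). Those are rates of treatment-emergent SAEs on combination tablets after about 21 weeks' median exposure, not rates of pre-dose events turning serious. The protocol's own Phase 1b hepatitis B study reports no SAEs. Neither gives the figure needed.

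**Conclusion.** The SAP definition contradicts Protocol 8.6.3 on two of four routes, and the change is not declared. As written, an AE with a complete pre-dose onset date that worsens or becomes serious on blinded drug, without leading to discontinuation, is missing from the treatment-emergent summaries and present only in the listings.

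The number of such events cannot be derived from the documents and is probably small. It is close to none if sites open a new AE record dated at the worsening. It is larger, up to all such events that did not stop treatment, if original onset dates are kept. Which of these applies is an assumption either way, since the eCRF convention is not given. The documents do not support any claim that a material share of AEs or SAEs is lost, or that one arm is favoured.

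**What to change.** In SAP 7.1.6.1, add the two protocol routes for the double-blind phase: an AE record with onset before the first blinded dose is treatment-emergent if its severity grade rises, or it changes from non-serious to serious, between the first and last blinded dose.

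In the same place, state how this is identified in the data. Where the eCRF dates changes in grade or seriousness, use those dates. Where it holds only one grade and one serious flag per record, the worsening must appear as a new AE record dated at the worsening, which the existing onset rule then counts.

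Noting the narrower definition in SAP 7.11 would make it visible but would leave the counts dependent on how each site dates an event, so it is the weaker remedy.

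The cost is SAP wording, one more derivation rule, and a check of what the eCRF records. AE counts may rise slightly.
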